3.9.1.2 Sample Size and Power for Testing the Secondary Efficacy Hypothesis

The power corresponding to the decision rule that will be implemented in testing the secondary efficacy hypothesis is based on a fixed-event design. The secondary efficacy hypothesis will be tested when a total of ≥ 15 CMVi cases in the combined V160 2-dose and placebo arms have been observed (see [Figure 1](#) in Section 3.7). When the secondary efficacy hypothesis is tested based on a total of ≥ 15 CMVi cases, the study has $>85\%$ power to demonstrate that the efficacy of a V160 2-dose regimen compared to placebo to prevent CMVi is $>0\%$ if the underlying vaccine efficacy is $\geq 85\%$ at an overall one-sided Type 1 error $\leq 2.5\%$ (see [Table 4](#)). The calculations are based on an exact method under a large sample Poisson distribution assumption proposed by Chan and Bohidar (1998) [1] and carried out using the R software.

This study will randomize 700 participants into the V160 2-dose regimen and 700 into the placebo regimen. Under the same assumptions governing the accumulation of CMVi cases in the V160 3-dose and placebo arms, a total of 15 CMVi cases in the combined V160 2-dose and placebo arms are projected to be accumulated in ≈ 18 to 19 months; and a total of 24 in ≈ 3 years.

It is possible that at the time when CMVi cases are counted to determine whether a total of 15 cases have been accrued in the combined V160 2-dose and placebo arms, the actual CMVi cases accumulated will already be greater than 15. In such an eventuality, the testing of the secondary efficacy hypothesis will be conducted based on the actual number of cases accrued (eg, 16, or 17, or some other count). [Table 4](#) also shows the operating characteristics of decision rules that will be used in the eventuality that the testing of the secondary efficacy hypothesis is conducted at a total case count greater than 15.

Table 4 Decision Rule and Corresponding Type 1 Error and Power for Testing the Secondary Efficacy Hypothesis of VE >0% Against CMVi (2-Dose Regimen vs. Placebo)

| Analysis Time Point | Total Cases Accrued | Case Split for Success (Vacc:Pbo) | VE (95% CI) | Type I Error | True Vaccine Efficacy | | | | | |
|---------------------|---------------------|-----------------------------------|-------------------|--------------|-----------------------|-------|-------|-------|-------|-------|
| | | | | | 70% | 75% | 80% | 85% | 90% | 95% |
| | | | | | Power | | | | | |
| Final | 15 | ≤3 : ≥12 | 75.0 (7.4, 95.5) | 1.8% | 53.2% | 64.8% | 76.8% | 87.8% | 95.9% | 99.5% |
| | 16 | ≤3 : ≥13 | 76.9 (16.0, 95.8) | 1.1% | 47.7% | 59.8% | 72.9% | 85.4% | 94.9% | 99.4% |
| | 17 | ≤4 : ≥13 | 79.2 (0.4, 92.7) | 2.5% | 64.7% | 75.8% | 86.0% | 93.9% | 98.5% | 99.9% |
| | 18 | ≤4 : ≥14 | 71.4 (9.0, 93.2) | 1.5% | 59.6% | 71.6% | 83.2% | 92.5% | 98.1% | 99.9% |
| | 19 | ≤4 : ≥15 | 73.3 (16.3, 93.6) | 1.0% | 54.5% | 67.3% | 80.1% | 90.9% | 97.6% | 99.8% |
| | 20 | ≤5 : ≥15 | 66.7 (3.5, 90.5) | 2.1% | 69.3% | 80.4% | 89.8% | 96.2% | 99.3% | 100% |
| | 21 | ≤5 : ≥16 | 68.8 (10.7, 91.0) | 1.3% | 64.8% | 76.9% | 87.7% | 95.3% | 99.1% | 100% |
| | 22 | ≤5 : ≥17 | 70.6 (16.9, 91.5) | 0.8% | 60.2% | 73.3% | 85.3% | 94.2% | 98.8% | 100% |
| | 23 | ≤6 : ≥17 | 64.7 (6.2, 88.6) | 1.7% | 73.2% | 84.0% | 92.5% | 97.7% | 99.7% | 100% |
| | 24 | ≤6 : ≥18 | 66.7 (12.3, 89.2) | 1.1% | 69.1% | 81.1% | 90.9% | 97.1% | 99.6% | 100% |
| | 25 | ≤7 : ≥18 | 61.1 (2.4, 86.3) | 2.2% | 79.8% | 89.1% | 95.5% | 98.8% | 99.9% | 100% |
| | 26 | ≤7 : ≥19 | 63.2 (8.5, 86.9) | 1.4% | 76.4% | 86.9% | 94.5% | 98.5% | 99.8% | 100% |
| | 27 | ≤7 : ≥20 | 65.0 (13.8, 87.5) | 1.0% | 72.8% | 84.4% | 93.2% | 98.1% | 99.8% | 100% |
| | 28 | ≤8 : ≥20 | 60.0 (5.2, 84.8) | 1.8% | 82.2% | 91.0% | 96.7% | 99.3% | 99.9% | 100% |
| | 29 | ≤8 : ≥21 | 61.9 (10.5, 85.4) | 1.2% | 79.1% | 89.2% | 95.9% | 99.1% | 99.9% | 100% |
| | 30 | ≤9 : ≥21 | 57.1 (2.4, 82.7) | 2.1% | 86.7% | 93.9% | 98.0% | 99.6% | 100% | 100% |
| | 31 | ≤9 : ≥22 | 59.1 (7.6, 83.4) | 1.5% | 84.2% | 92.5% | 97.5% | 99.5% | 100% | 100% |
| | 32 | ≤9 : ≥23 | 60.9 (12.2, 84.1) | 1.0% | 81.5% | 91.0% | 96.9% | 99.4% | 100% | 100% |
| | 33 | ≤10 : ≥23 | 56.5 (5.0, 81.5) | 1.8% | 88.1% | 94.9% | 98.5% | 99.8% | 100% | 100% |
| | 34 | ≤10 : ≥24 | 58.3 (9.6, 82.2) | 1.2% | 85.9% | 93.8% | 98.1% | 99.7% | 100% | 100% |
| 35 | ≤11 : ≥24 | 54.2 (2.8, 79.7) | 2.0% | 91.1% | 96.6% | 99.1% | 99.9% | 100% | 100% | |

CI = Confidence interval; VE = Vaccine efficacy.

3.9.2 Sample Size and Power for Safety Analyses

Testing of hypotheses relating to safety will not be conducted in this study. Thus, power and Type 1 error considerations relating to safety analyses are not applicable in this study.

The probability of observing a specific AE in specific treatment arms of this study depends on the number of vaccinated participants with safety follow-up and the underlying incidence of that specific AE in the study population. In each treatment arm, assuming that all 700 participants randomized into the study will have safety follow-up, then there is a >99% chance of observing at least one specific AE if the incidence of that AE is at least 1 in every 150 participants; >90% chance if the incidence is at least 1 in every 300 participants. If no vaccine-related SAEs are observed among the 700 participants randomized in a specific V160 treatment arm, this study will provide 97.5% confidence that the underlying percentage of participants with vaccine-related SAE is $\leq 0.5\%$ (1 in every 200 participants) among V160 vaccinated participants in that V160 arm. This is based on calculation of a 1-sided 97.5% upper confidence limit of a binomial proportion using the exact binomial method of Clopper and Pearson [3] and was done using PASS 2008. For a sample size of 700 per treatment arm, Table 5 provides the critical split of participants with AEs between V160 and placebo arms for which it will be possible to state with 95% confidence that the risk difference (defined as percent in V160 dose regimen group minus percent in placebo) excludes 0%. For a specific AE, given a sample size of 700 per arm, the minimum total number of participants with AEs for which it is possible to state with 95% confidence that the risk difference excludes 0% is 5. As stated in Section 3.6.3, AEs observed in at least 7 participants (representing 1% of N=700 participants per group) in any vaccination group will be categorized as a Tier 2 event. The 95% CIs of the percentage point differences were calculated using the Miettinen and Nurminen method [2].

Table 5 Critical Counts of Participants with Adverse Events in V160 and Placebo Arms Resulting in the Lower Bound of 95% CI Estimate of Risk Difference to be >0%

| Observed Count of Participants with Adverse Events | | | Risk Difference [†] (V160 – Placebo) | |
|----------------------------------------------------|--------------|-----------------|-----------------------------------------------|---------------------|
| Total | V160 (N=700) | Placebo (N=700) | Percentage Points [‡] | 95% CI [§] |
| 5 | 5 | 0 | 0.7% | (0.1%, 1.7%) |
| 6 | 6 | 0 | 0.8% | (0.3%, 1.8%) |
| 7 | 7 | 0 | 1.0% | (0.4%, 2.0%) |
| 8 | 7 | 1 | 0.9% | (0.1%, 1.9%) |
| 9 | 8 | 1 | 1.0% | (0.2%, 2.1%) |
| 10 | 9 | 1 | 1.1% | (0.3%, 2.3%) |
| 11 | 9 | 2 | 1.0% | (0.1%, 2.2%) |
| 12 | 10 | 2 | 1.1% | (0.2%, 2.4%) |
| 13 | 11 | 2 | 1.3% | (0.4%, 2.5%) |
| 14 | 11 | 3 | 1.1% | (0.1%, 2.4%) |
| 15 | 12 | 3 | 1.3% | (0.3%, 2.6%) |
| 16 | 13 | 3 | 1.4% | (0.4%, 2.8%) |
| 17 | 13 | 4 | 1.3% | (0.2%, 2.6%) |
| 18 | 14 | 4 | 1.4% | (0.3%, 2.8%) |
| 19 | 15 | 4 | 1.6% | (0.4%, 3.0%) |
| | 14 | 5 | 1.3% | (0.1%, 2.7%) |

| Observed Count of Participants with Adverse Events | | | Risk Difference [†] (V160 – Placebo) | |
|-------------------------------------------------------------------------------------------------------------------------------------------------------------------------------------------------------------------------------------------------------------------------------------------------------------------------------------------------------------------|--------------|-----------------|-----------------------------------------------|---------------------|
| Total | V160 (N=700) | Placebo (N=700) | Percentage Points [‡] | 95% CI [§] |
| 20 | 15 | 5 | 1.4% | (0.2%, 2.9%) |
| [†] Defined as percent of participants in the V160 group with adverse events minus the corresponding percent in the placebo group. [‡] Calculated as $100\% \times (V160 - Placebo) \div 700$. [§] Calculated based on the Miettinen and Nurminen method. N = Number of participants randomized. CI = Confidence interval | | | | |

3.10 Subgroup Analyses and Effect of Baseline Factors

To determine whether VE is consistent across various subgroups associated with specific baseline participant characteristics, the estimate of the VE (with a nominal 95% CI) for the primary efficacy endpoint (comparing 3-dose regimen versus placebo) and for the secondary efficacy endpoint (comparing 2-dose regimen versus placebo) will be estimated and plotted within each subgroup. Subgroup assessments of VE will be conducted for the following baseline participant characteristics:

- Age category (≤ 21 vs. > 21 years)
- Race (white, non-white)
- Region (US, Ex-US)

For each of the primary and secondary efficacy endpoints, a Forest plot will be produced, which provides the estimated point and 95% CI estimates of VE across the subgroups associated with specific baseline participant characteristics listed above. The consistency of VE across subgroups will be assessed descriptively based on these Forest plots.

3.11 Compliance

3.11.1 Adherence to Scheduled Vaccinations

Compliance to scheduled vaccinations in this study is defined as receipt of all 3 vaccinations of either V160 or placebo. To summarize compliance, the numbers of participants who receive each vaccination will be tabulated. For each of vaccination visits 2 and 3, histograms of the time (in days) of administration of the vaccine or placebo relative to the target vaccination visit will be provided.

3.11.2 Adherence to Scheduled Self-Collection of Urine and Saliva Samples

Accurate and reliable ascertainment of the primary and secondary efficacy endpoints (ie, incidence of CMVi) will depend on compliance of study participants to the self-collection of urine and saliva samples based on the schedule indicated in Section 2. Thus, compliance of study participants to the self-collection of urine and saliva samples will be assessed as follows.

On a participant-level (say the i -th participant among the $N=2100$ study participants), percent compliance (denoted by P_i) of a study participant to the self-collection of urine and/or saliva samples will be calculated as:

$$P_i = \frac{n_i}{M_i} \times 100\%$$

where

n_i = number of visits for which either a urine or saliva sample was received from the study participant;

M_i = total number of study visits throughout the study for which a urine or saliva sample is expected to be received from the study participant. This number will vary based on the time when the study participant enters the study and the time when the study ends.

For each of the V160 3-dose, V160 2-dose, and placebo arms, point and 95% CI estimates of the geometric mean of the participant-level percent compliance P_i will be calculated to summarize the vaccination group-level compliance of study participants to the self-collection of urine and saliva samples.

This assessment of compliance of study participants to the self-collection of urine and saliva samples will be conducted in both the PPE and FAS analysis populations.

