| Adverse event monitoring | X | X | X | X | X | | 
Screening to randomization: All AEs, SAEs, and other reportable events that cause the participant to be excluded from the trial or are the result of a protocol-specified intervention are to be reported.
 
Randomization through 14 days following Dose 3: AEs (serious and non-serious) are to be reported from Days 1 through 14 following each vaccination. SAEs, deaths, other reportable events (ie, cancer, overdose, pregnancy, and infant SAEs) are to be reported throughout the duration of an individual's study participation. Exposure during breastfeeding is to be reported from Day 1 through Month 7.
 |
| Review of eVRC data | | | X | X | X | | |
| Reminder contact for urine/saliva self-collection and pregnancy status | | | | | | X | |
| Urine and saliva for CMV | | X | Collected monthly | | | | Self-collected by participant starting at Day 1 (prior to vaccination) and then continue monthly through ~Month 36 or beyond, depending on event accrual |

Vacc = Vaccine; eVRC = Electronic vaccination report card; NAbs = neutralizing antibodies; β-hCG = Human chorionic gonadotropin; IgG = immunoglobulin G; IFN-γ = Interferon gamma; ELISA = Enzyme-linked immunosorbent assay; PBMC = peripheral blood mononuclear cell; DNA = Deoxyribonucleic acid; CMV = Cytomegalovirus; AE = Adverse event; SAE = Serious adverse event

2.2 Schedule of Activities: Follow-up Period Through Approximately Month 36 (Approximate Time Point to Reach Cases Required for Primary Endpoint Assessment)

| Trial period | Follow-up period | | | | | Reminder contacts (monthly) | Notes |
|------------------------------------------------------------------------------------------------------------------------------------------------|-------------------------------|---------------------------------|-------------------------------|---------------------------------|--------------------------------|-----------------------------|-----------------------------------------------------------------------------------------------------------------------------------------------------------------------------------------------------------------------------------------------------------------------------------------------------------------------------------------------|
| Visit number/title | Visit 6 Month 12 Year 1 | Visit 7 Month 18 Year 1.5 | Visit 8 Month 24 Year 2 | Visit 9 Month 30 Year 2.5 | Visit 10 Month 36 Year 3 | | |

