9.2.1.1.2 CMVi Case Detection

At Visit 2 (Day 1), participants will be trained on proper saliva and urine sample collection procedures using the self-collection kits provided. The first set of samples will be collected on site by the participant. All other samples will be collected monthly, from Month 1 to approximately Month 36, by the participant outside of the study site (eg. at home or place of employment) or at scheduled site visits (when applicable), as indicated in the SoA.

In addition to on-site training, instructional materials will be provided to the participant to use as a reference. Participants will contact the site with any questions or concerns they have regarding the self-collection process. Reminder contacts will be made monthly to the participants, to prompt their collection of samples. Receipt of the samples will be tracked in real-time in order to provide feedback to the site. The site will contact and re-train participants who are missing samples or submitting samples which are unacceptable for testing. Detailed instructions will be provided to the site for monitoring self-collection and sample handling.

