10.11.2 Adherence to Scheduled Self-Collection of Urine and Saliva Samples

Accurate and reliable ascertainment of the primary and secondary efficacy endpoints (ie, incidence of CMVi) will depend on compliance of study participants to the self-collection of urine and saliva samples based on the schedule indicated in Section 2. Thus, compliance of

study participants to the self-collection of urine and saliva samples will be assessed as follows.

On a participant-level (say the i -th participant among the $N=2100$ study participants), percent compliance (denoted by P_i) of a study participant to the self-collection of urine and/or saliva samples will be calculated as:

$$P_i = \frac{n_i}{M_i} \times 100\%$$

where

n_i = number of visits for which either a urine or saliva sample was received from the study participant;

M_i = total number of study visits throughout the study for which a urine or saliva sample is expected to be received from the study participant. This number will vary based on the time when the study participant enters the study and the time when the study ends.

For each of the V160 3-dose, V160 2-dose, and placebo arms, point and 95% CI estimates of the geometric mean of the participant-level percent compliance P_i will be calculated to summarize the vaccination group-level compliance of study participants to the self-collection of urine and saliva samples.

This assessment of compliance of study participants to the self-collection of urine and saliva samples will be conducted in both the PPE and FAS analysis populations.

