3.5 Analysis Populations

3.5.1 Efficacy Analysis Populations

Per Protocol Efficacy (PPE)

The PPE population will serve as the primary population for the evaluation of VE and for testing the primary and secondary efficacy hypotheses. To be eligible for inclusion in the PPE population, randomized study participants must satisfy the following criteria:

- CMV seronegative at Day 1 and CMV negative by PCR for non-vaccine strain virus from post Day 1 through Month 7
- Have received all 3 injections/vaccinations within the vaccination visit window specified in the SoA (Section 2)
- At any time from Day 1 through Month 7, did not have events, deviations from protocol, or engaged in activities that are deemed by the study Clinical Director to potentially interfere with the evaluation of efficacy or immune response to injections of V160.

Participants whose CMV status by PCR post Day 1 through Month 7 is not evaluable will be ineligible for inclusion in the PPE population. The categories of events, deviations from protocol, or activities that are deemed by the study Clinical Director to potentially interfere with the evaluation of efficacy or immune response to injections of V160 include the following:

1. Participant was not serologically confirmed as CMV seronegative (based on CMV IgG) during screening;
2. Participant was immunocompromised or had been diagnosed as having a congenital or acquired immunodeficiency, human immunodeficiency virus (HIV) infection, lymphoma, leukemia, systemic lupus erythematosus, rheumatoid arthritis, juvenile rheumatoid arthritis, inflammatory bowel disease, or other autoimmune condition at any time between Day 1 to Month 7;
3. Participant had previously received a non-study CMV vaccine.
4. Participant received systemic corticosteroids (equivalent ≥ 2 mg/kg total daily dose of prednisone or ≥ 20 mg/d for persons weighing >10 kg) for ≥ 14 consecutive days and has not completed treatment at least 30 days prior to any vaccination dose;

5. Participant received systemic corticosteroids exceeding physiologic replacement doses (approximately 5 mg/d prednisone equivalent) within 14 days prior to any vaccination dose;
6. Participant received any anti-viral agent with proven or potential activity against CMV (e.g. letermovir, ganciclovir, valganciclovir, foscarnet, cidofovir, valacyclovir) two weeks prior to any vaccination dose or likely to receive such an agent within two weeks after any vaccination dose.

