7. Participant was receiving or has received in the year prior to randomization immunosuppressive therapies including but not limited to rapamycin (also sirolimus), tacrolimus (also FK-506 or Fujimycin), or other therapies used for solid organ/cell transplant, radiation therapy, immunosuppressive/cytotoxic immunotherapy, chemotherapy and other immunosuppressive therapies known to interfere with the immune response.
8. Participant used topical tacrolimus within 2 weeks before or after any vaccination dose;
9. Participant received study clinical material in a sequence that is different from the sequence corresponding to the vaccination group to which the participant was randomized into (i.e., incorrect vaccination sequence or cross-treatment).
10. Participant was administered improperly stored study clinical material that was deemed unacceptable for use.
11. Participant received improperly reconstituted study clinical material that may affect efficacy and/or safety.

Full Analysis Set (FAS)

The FAS will serve as a supportive analysis population for the evaluation of VE. The FAS population consists of all randomized participants who received at least 1 dose of the correct clinical material corresponding to the treatment regimen the participants were randomized into.

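### Sampling compliance is summarised by a geometric mean with no rule for zero and a denominator that, as written, runs past withdrawal, so the table would understate the share of expected collections received, mainly in the FAS

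*Combined protocol and SAP*

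**What the plan says.** Both the sSAP (3.11.2) and the protocol (10.11.2) define compliance for each participant as P_i = 100 × n_i/M_i.

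- The numerator n_i is the "number of visits for which either a urine or saliva sample was received from the study participant".
- The denominator M_i is the number of study visits at which a sample is expected. The only stated sources of variation are entry and study end: "This number will vary based on the time when the study participant enters the study and the time when the study ends".
- The arm-level summary is a point estimate and 95% CI of the "geometric mean of the participant-level percent compliance". It "will be conducted in both the PPE and FAS analysis populations".

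The sampling schedule (protocol 2.1) is: "Self-collected by participant starting at Day 1 (prior to vaccination) and then continue monthly". On Day 1 the collection is supervised (protocol 9.2.1.1.2): "The first set of samples will be collected on site by the participant".

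The two populations differ in what they require. For the FAS: "The FAS population consists of all randomized participants who received at least 1 dose of the correct clinical material". For the PPE population: "Participants whose CMV status by PCR post Day 1 through Month 7 is not evaluable will be ineligible for inclusion in the PPE population".

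The compliance section gives no rule for P_i = 0. By contrast, sSAP 3.6.2 does give a substitution rule (half the LLOQ) before logging antibody titers.

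**The concern.** A geometric mean suits positive, right-skewed quantities such as titers. Compliance percentages are bounded at 100, bunched near the top, and have a lower tail that can reach zero. On the log scale that tail carries most of the weight.

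Two features of the definition make the tail longer. A woman who leaves early keeps her full denominator on the plain reading of M_i, so her P_i reflects how long she stayed rather than how well she sampled. And a single zero collapses the statistic.

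The plan introduces this summary by saying that reliable ascertainment of the primary and secondary endpoints depends on participants' sampling compliance. Readers will use the table to judge whether coverage was adequate and similar across arms. The quantity they need is the share of expected collections received, and a geometric mean of P_i does not estimate it.

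**Working it through.** The documents give no compliance figure to reproduce, so the check compares summary statistics under the plan's own design inputs.

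**Inputs from the documents.** 700 per arm and loss to follow-up of about 5% to 10% per year (sSAP 3.9.1.1). Day 1 then monthly to about Month 36 gives M = 1 + 36 = 37. An 18-month enrolment period in a 3-year study gives late entrants about 18 months, so M = 1 + 18 = 19.

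**Assumptions not in the documents.** 95% compliance while in the study, Day 1 always received, exponential drop-out, and M_i not cut at withdrawal.

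**Formulas.** GM = exp[(1/N) Σ ln P_i]; AM = (1/N) Σ P_i.

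**Step 1: one zero.** With 699 women at 95% and one at 0%, AM = 699 × 95/700 = 94.9%. GM = 0, and the log-scale SD and CI are undefined.

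**Step 2: can a zero occur?**
- PPE: no, because PCR status after Day 1 through Month 7 must be evaluable.
- FAS with Day 1 counted: the floor is normally 1/37 = 2.7%.
- FAS with Day 1 not counted: the chance of leaving before Month 1 is 1 − (1 − d)^(1/12), which is 0.00427 at d = 5% and 0.00874 at d = 10%. Times 700, that is about 3 to 6 women per arm. The chance of at least one zero is 1 − (1 − 0.00427)^700 = 95.0%, or 99.8% with 0.00874.

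The compliance section refers to the Section 2 schedule, which includes Day 1, but does not say outright that Day 1 enters n_i and M_i.

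**Step 3: sensitivity to drop-outs at the floor.** With m of 700 women at 2.7% and the rest at 95%, GM = exp{[(700 − m) ln 95 + m ln 2.7]/700}.

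| m | GM | AM |
|---|---|---|
| 1 | 94.5 | 94.9 |
| 7 | 91.7 | 94.1 |
| 35 | 79.5 | 90.4 |
| 70 | 66.5 | 85.8 |

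If one arm had 7 such women and another 35, the arms would differ by 91.7 − 79.5 = 12.2 points on the GM and 94.1 − 90.4 = 3.7 on the AM.

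**Step 4: drop-out spread over follow-up.** 2000 simulated arms of 700. The PPE rows keep only women still in the study at Month 7.

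| Population, M | Loss/yr | GM | AM | Gap | Median |
|---|---|---|---|---|---|
| FAS, 37 | 5% | 82.6 | 88.2 | 5.6 | 94.6 |
| FAS, 37 | 10% | 72.1 | 81.6 | 9.5 | 94.5 |
| FAS, 19 | 5% | 88.8 | 91.7 | 2.9 | 94.7 |
| FAS, 19 | 10% | 82.8 | 88.1 | 5.3 | 94.7 |
| PPE, 37 | 5% | 88.5 | 90.6 | 2.1 | 94.6 |
| PPE, 37 | 10% | 82.4 | 86.1 | 3.7 | 94.6 |

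All women here share one M, so the pooled proportion received equals the AM. With M_i ended at withdrawal, every summary would sit close to the assumed 95%. The shortfall below 95% in the GM and AM columns is therefore retention, not sampling behaviour.

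**Step 5: does P_i reach the efficacy analysis?** A case is PCR detection in one saliva or urine sample (protocol 9.2.1.1.1). VE uses case counts and person-years (sSAP 3.6.1). PPE membership uses PCR evaluability, dosing and deviations (sSAP 3.5.1). The decision rules reproduce with no compliance input: P(X ≤ 3 | n = 15, π = 0.5) = (1 + 15 + 105 + 455)/32768 = 1.76%, stated as 1.8%. With π = 0.15/1.15 (VE 85%) the power is 87.85%, stated as 87.8%.

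**The case against.** The strongest reply is that this is a descriptive table and nothing depends on it numerically. That stands. A reader might infer that endpoint ascertainment itself will be wrong, but Step 5 shows that P_i enters no case, population, estimate or decision. The plan ties ascertainment to what participants do, not to this statistic. Sample receipt is also tracked in real time, with re-training of participants whose samples are missing or unacceptable (protocol 9.2.1.1.2).

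A reader might also infer that a handful of drop-outs dominates the figure. Short of an exact zero, they do not. Seven women at the floor put the GM only 2.4 points below the AM, and a large shift needs roughly 5% of an arm. A scenario with 10% of the arm at the floor is extreme, because it has all of them leaving just after Day 1, whereas the plan's loss rate is per year.

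Zeros cannot occur in the PPE population, and they are unlikely in the FAS if the on-site Day 1 sample counts.

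The denominator is partly a matter of reading. M_i counts samples that are expected, and protocol 8.2 says withdrawn women are no longer followed at scheduled visits, so one could argue that none are expected from them. But the text names only entry and study end, and protocol 8.3 does not treat an uncontactable woman as lost until her last scheduled visit. Both favour the longer denominator. At best the point is ambiguous.

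Counting a month as compliant when either matrix arrives is defensible, since one positive sample of either kind makes a case. It is not treated as a defect here.

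**Conclusion.** The point holds as a minor one about a descriptive summary. The prescribed statistic is a poor estimate of the share of expected collections received, has no rule for zero, and on the plain reading of M_i confounds retention with sampling behaviour. At the plan's loss rates the FAS geometric mean falls about 6 to 10 points below the arithmetic mean for women with 37 scheduled collections, about 3 to 5 points for those with 19, and about 2 to 4 points in the PPE population with 37. The direction is towards understating compliance, and differences in early drop-out between arms are magnified.

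These sizes rest on the assumed 95% in-study compliance, exponential drop-out, Day 1 always received, and M_i not stopping at withdrawal. If M_i does stop at withdrawal, most of the gap disappears and the undefined zero case is the main remaining weakness. The documents do not support any effect on case detection, PPE membership, VE or the decision rules.

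**What to change.** In sSAP 3.11.2:

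- Replace the geometric mean with the pooled proportion of expected monthly collections received, together with the arithmetic mean and median of P_i, by arm in the PPE and FAS populations.
- State that the Day 1 collection counts in both n_i and M_i.
- Define M_i as ending at withdrawal, and give a second version with M_i running to study end. The first describes sampling behaviour; the second describes coverage of the planned follow-up.
- Optionally, add a row for months in which both matrices were received.

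All of these summaries are defined when P_i = 0, so no substitution rule is needed. The change is non-confirmatory, and sSAP Section 1 allows such changes to be documented in the sSAP before unblinding and final database lock. It needs no new data and touches no hypothesis or decision rule. The cost is a few lines of text and a slightly longer table.
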